### **8.5 Twenty minute time-out if patients remains in cardiac arrest**

Twenty minutes after the start of resuscitation by a healthcare provider a team time out will be called. Cardiopulmonary resuscitation will continue during this time out.

The pre-hospital consultant will present the patient using the Situation Background Assessment Recommendation (SBAR) format. The assessment will include reciting the inclusion and exclusion criteria in a challenge response manner. If the team considers that there are no exclusion criteria met then the ECMO consultants will proceed to cannulate the patient's femoral artery and vein and commence ECMO support. In the interval between 20 minutes of resuscitation and ECMO support, no more epinephrine (adrenaline) boluses will be administered. If chest compressions must be interrupted for insertion of the cannulae then this will be for no more than ten seconds (as timed by the consultant in pre-hospital medicine).

If an exclusion criterion is identified then any wires present at that point will be used to insert 6 Fr angiography sheaths into the femoral artery and/or vein which may facilitate on-going care. The team will then continue to support LAS as required. All patients will be followed up for adverse events related to the insertion of guidewires for seven days following the cardiac arrest. No other data, other than that included in the screening log, will be collected for these patients.

If cannulation cannot be achieved within 60 minutes then further attempts will not be continued and the patient reviewed and consideration made to declare life extinct or transport the patient under ongoing CPR to the nearest emergency department.

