**Principal Investigator Name:** **[name]**

**Signature:** 

**Date:** **02 March 2022**

### 3. Summary and synopsis

Short Title	Sub30
Methodology	Feasibility study of a complex intervention
Research Sites	Barts Health NHS Trust London Ambulance Service NHS Trust
Objective/Aims	To establish whether a pre-hospital advanced physician/ paramedic cardiac arrest team that is ECMO capable can establish ECMO flow within 30 minutes of collapse
Number of participants	6 patients who are cannulated for ECMO
Inclusion and exclusion criteria	
Male and female patients with a known or visible age of 18 to 65 years who:
 
 
have a witnessed out-of-hospital cardiac arrest
 
a presumed cardiac aetiology to their cardiac arrest
 
receive bystander chest compressions within 3 minutes
 
remain in cardiac arrest at 20 minutes following collapse or fail to sustain ROSC in the pre-hospital setting
 
 
The following patients will not be suitable for ECMO:
 
 
Identified as or visibly less than 18 years or greater than 65 years
 
Known or visible advanced pregnancy (when resuscitative hysterotomy should be performed)
 
Evidence from others present at the scene or patient examination that ECMO unlikely to benefit patient (e.g. advanced frailty, advanced malignancy, ...).
 
No signs of life (physical movement or breathing) AND evidence of ineffective chest compressions suggested by: 
 
Absence of electrical activity OR
 
End tidal carbon dioxide level of less than 1.3 kPa (10 mmHg)
 
 
 
 
Out-of-hospital cardiac arrest encompasses both those who arrest prior to the emergency services being called and those who are witnessed to arrest by the emergency services. For the purpose of this study patients who suffer their first cardiac arrest whilst in transit to hospital will not be included.

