## 5.3 Primary outcome

The primary endpoint is the proportion of patients successfully established with pre-hospital ECPR within 30 minutes of collapse. The time of collapse will be defined as the time the call to the emergency services commences or the time that a patient was witnessed to suffer a cardiac arrest if this happens in front of the emergency services.

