## 6. Study population

### 6.1 Inclusion criteria

Male or female patients with a known or visible age of 18 to 65 years who:

- have a witnessed out-of-hospital cardiac arrest
- a presumed cardiac aetiology to their cardiac arrest
- receive bystander chest compressions within 3 minutes
- remain in cardiac arrest at 20 minutes following collapse or fail to sustain ROSC in the pre-hospital setting

Out-of-hospital cardiac arrest encompasses both those who arrest prior to the emergency services being called and those who are witnessed to arrest by the emergency services. For the purpose of this study patients who suffer their first cardiac arrest whilst in transit to hospital will not be included.

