## **8.3 ECPR Pre-hospital team roles and responsibilities**

The pre-hospital ECPR team will endeavour to achieve ROSC by delivering and supporting others in delivery of ALS to the patient. They will:

- introduce the ECPR team to any on scene healthcare resources
- manage the cardiac arrest following London Ambulance Service and Resuscitation Council ALS Guidelines
- seek ROSC by addressing reversible causes, ensuring advanced airway management and optimising resuscitation including automated mechanical compressions
- administer intravenous fluids to aid percutaneous cannulation by the ECMO team as required
- manage the pre-hospital environment and ensure team safety
- establish 360 degrees access to the patient
- establish collateral history about the patient, the collapse, and the timings of resuscitation attempts
- prepare for team timeout if cardiac arrest is refractory at 20 minutes of resuscitation by healthcare professionals

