## **8.4 ECMO consultants' initial roles and responsibilities**

The ECMO consultants will establish a sterile surgical area in the patient's groin and using real-time ultrasound guidance to percutaneously insert guide wires into the patient's femoral artery and vein. The position of wires in the aorta and inferior vena cava respectively will be confirmed using

subcostal/trans-hepatic ultrasound. They will also complete the priming of the CardioHelp circuit so it is ready for use. If chest compressions must be interrupted for insertion of the needle/guidewire then this will be for no more than ten seconds (as timed by the consultant in pre-hospital medicine) and attempts made to coordinate these with any pulse checks.

If ROSC is achieved prior to 20 minutes of resuscitation then any wires present at that point will be used to insert 6Fr angiography sheaths into the femoral artery and/or vein to facilitate care at the Heart Attack Centre. The team will then continue to support LAS as required to provide standard post-resuscitation care and expedited transfer to the nearest Heart Attack Centre.

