### 10.2 Methods of Analysis

Data will be analysed using a combination of Excel for Mac 2016 (Microsoft Corporation), Prism 5 (GraphPad software) and R. Summary data will be presented as a median and range for all six patients. Categorical data will be presented as raw data.

Patient mortality will be compared to other patients who were managed by LAS on non-study days. These data are stored in a bespoke Cardiac Arrest database, for which London Ambulance Service NHS Trust is the Data Controller. Only patients cared for concurrently with this study will be used for matching. London Ambulance Service NHS Trust will provide these data to the Chief Investigator after the last patient has been enrolled.

Patients will be matched based on their likelihood of receiving ECMO on a one to many basis. Potential matches will be first screened for the study inclusion and exclusion criteria. A priori defined factors that may be used to estimate this likelihood of receiving are:

- age (closest match to 5 years)
- time of first LAS resource attendance on scene (closest match to 5 minutes)
- presumption of a cardiac aetiology to the arrest

Three techniques will be used in matching – individual matching, propensity score matching and GenMatch matching. Matching will be undertaken with replacement. Missing data will not be imputed.

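### The refractory-arrest criterion runs from collapse but cannulation is released on a later clock, so controls screened on the criterion as written can include patients with sustained ROSC whom a study day would not have cannulated

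*Protocol*

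**What the plan says.** **Eligibility clock.** The synopsis and Protocol 6.1 admit patients who "remain in cardiac arrest at 20 minutes following collapse or fail to sustain ROSC in the pre-hospital setting". Under Protocol 5.3, collapse is the start of the emergency call, "or the time that a patient was witnessed to suffer a cardiac arrest if this happens in front of the emergency services". Section 6.1 expressly includes "those who are witnessed to arrest by the emergency services".

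**Treatment clock.** Protocol 8.3 has the team "prepare for team timeout if cardiac arrest is refractory at 20 minutes of resuscitation by healthcare professionals". Protocol 8.5 agrees: "Twenty minutes after the start of resuscitation by a healthcare provider a team time out will be called". Protocol 8.4 deals with earlier ROSC: "If ROSC is achieved prior to 20 minutes of resuscitation then any wires present at that point will be used" to place angiography sheaths, and the patient then goes to a Heart Attack Centre with standard care and no ECMO.

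**SAP clocks.** SAP section 5 refers to 20 minutes without an origin. SAP 4.1.1 counts from the start of resuscitation without saying by whom.

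**Controls.** Protocol 10.2 states: "Potential matches will be first screened for the study inclusion and exclusion criteria". SAP 4.1.3 and 8.1.5 follow the same approach. The matching factors are age and time of LAS attendance; the protocol also lists presumed cardiac aetiology. Survival is the only endpoint that SAP Table 3 assigns to controls.

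**The concern.** A cannulated patient has passed two gates: the collapse-based criterion and, for most patients, a later time-out. A control has to pass only the first, if 6.1 is applied as written. Anyone who regains and keeps a circulation between the two times is therefore removed from the treated side but allowed on the control side.

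Such patients probably survive more often than those still in arrest. Admitting them would tend to raise control survival and make ECPR look worse. The comparison matters because Protocol 4.5 and SAP 2.2 say the study should help to estimate the size of any outcome benefit for a later trial.

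**Working it through.** There is no sample-size or power figure to reproduce: six patients were chosen without a calculation (Protocol 10.1, SAP 3.8). The check has five parts.

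**1. Width of the gap.** Let t be the minutes from collapse (5.3) to the start of provider resuscitation. The time-out falls at t + 20 minutes from collapse and the criterion is judged at 20, so the gap is (t + 20) − 20 = t.

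| t (min) | Basis | Time-out, min from collapse | Gap (min) |
|---|---|---|---|
| 0 | arrest witnessed by the emergency services | 20 | about 0 |
| 3 | assumed | 23 | 3 |
| 5 | assumed | 25 | 5 |
| 7 | assumed | 27 | 7 |
| 8–10 | ECPR team first on scene, at its Protocol 4.5 objective | 28–30 | 8–10 |

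The documents give no arrival time for the first LAS crew.

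**2. One patient followed through the rules.** Take t = 5, with sustained ROSC at minute 23 from collapse.
- Protocol 6.1: in arrest at minute 20, so the criterion is met.
- On a study day: 23 − 5 = 18 minutes of provider resuscitation at ROSC, which is before the time-out, so 8.4 applies and there is no cannulation.
- On a non-study day: the patient passes 6.1. The 6.2 criterion that names the time-out needs no signs of life plus either absent electrical activity or low end-tidal carbon dioxide, so it does not remove a patient for having ROSC.
- Matching: age, attendance time and aetiology say nothing about continuing arrest. Matching on attendance may at most align t between patient and control.

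**3. What one such control can do.** SAP 8.1.5, read with the one-to-many matching of Protocol 10.2, is taken as up to five controls per patient, so at most 6 × 5 = 30 matches. Assume all are found and pooled simply.
- One survivor in place of one death: 1/30 = 3.3 percentage points.
- The same control used for two patients, under replacement: 2/30 = 6.7 points.
- One outcome among the treated patients: 1/6 = 16.7 points.

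The first two figures hold for any misclassified control from any cause. They do not measure how often this gap produces one.

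**4. Why no overall shift is claimed.** If a share q of controls has ROSC in the gap, with survival s1 against s0 in the rest, the shift is q(s1 − s0). None of these is in the documents. Purely as an illustration, with s0 = 5% assumed:
- q = 5%, s1 = 20%: 0.05 × 0.15 = 0.75 points.
- q = 20%, s1 = 40%: 0.20 × 0.35 = 7.0 points.

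The answer depends almost wholly on the assumed inputs.

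**5. Choice of proxy.** Suppose a crew arrives at minute 0 and the patient arrests at minute 15.
- Attendance + 20 screens at minute 20, after only 20 − 15 = 5 minutes of arrest.
- The later of attendance and collapse, + 20, screens at 15 + 20 = 35, after 35 − 15 = 20 minutes of arrest.

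**The case against.** The strongest reply is that the plan clearly means controls to be refractory. Protocol 10.2 matches on likelihood of receiving ECMO, and SAP 3.1 on suitability for ECPR. A patient with sustained ROSC before the time-out has essentially neither. Protocol 8.5 has the criteria recited at the time-out, and 7.4 places formal enrolment there. The intent therefore stands, but no listed factor or screening rule carries it out.

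A reader might infer that the time-out plays no part in control screening. That is too strong: 6.2 names it, so one exclusion criterion already needs a time-out moment for each control. It does not remove the patients at issue.

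A reader might also infer that the analysis is bound to the collapse clock. The SAP wording does not support that. An analyst working from SAP 4.1.1 and section 5 alone need not create the gap. The SAP leaves the choice open, whereas Protocol 6.1 read literally gives the wrong answer.

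Finally, the effect may be slight: six patients, no hypothesis tests (SAP 3.7), a primary endpoint that is not a matched comparison, and few survivors without disability after 20 minutes according to Protocol 11.4. All of this stands and sets the severity.

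**Conclusion.** The concern holds as a **minor** point. Confidence is high that the two clocks differ and moderate that this affects the controls, because that depends on how screening is carried out.

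If 6.1 is applied as written, the control group can include patients whose study-day equivalents would not be cannulated. The gap is about zero for arrests witnessed by the emergency services and otherwise equals the unstated time from call to provider start. The 8–10 minute figure applies only if the ECPR team arrives first; it is not a general estimate.

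A reader might infer that the survival comparison is materially biased against ECPR. The documents do not support that. The direction is an inference about survival after late ROSC, and neither the number of such controls nor their survival is given.

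Aligning the clocks leaves a second mismatch. Controls with ROSC between the time-out and the time ECMO would have flowed stay in, while the SAP treated population is cannulated patients. Protocol 10.1 instead counts patients in whom cannulation is attempted, so the documents differ on whether a study patient with ROSC during cannulation is among the six. As 8.5 allows attempts up to 60 minutes, this second interval may be longer than the first.

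**What to change.** 1. **Control screening (Protocol 10.2, SAP 8.1.5).** Require controls to be still in cardiac arrest 20 minutes after a healthcare provider starts resuscitation, or to have failed to sustain ROSC in the pre-hospital setting. Keep the second limb, so that controls who re-arrest are handled as in 6.1.
2. **Proxy.** Where the provider start time is not recorded, use the later of first LAS attendance and collapse (as in 5.3), and call it a proxy. Arrival is not the start of resuscitation and the first provider need not be LAS, so some misclassification remains.
3. **Data.** Ask for arrest time, ROSC time and any re-arrest in the single LAS transfer (Protocol 13.3). Report how many controls cannot be classified.
4. **Wording.** Put the synopsis, 6.1 and SAP section 5 on the same clock. Leave the 8.5 time-out unchanged.
5. **Limitation.** State the remaining mismatch for ROSC between time-out and ECMO flow, and the difference between the SAP treated population and Protocol 10.1.

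The cost is a few lines in a protocol amendment and SAP revision, and a few fields in a transfer already planned, provided LAS holds them. First attendance time is already a matching factor, and screening on 6.1 already needs each control's arrest status at 20 minutes. The change should be made before the data request, because only one transfer is foreseen.

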### **8.6 ECMO support**

Target parameters for initial ECMO support and the on-going care of the patient on ECMO are outlined in the ECMO Study Manual. ECMO support will endeavour to ensure perfusion of the vital organs whilst minimising any reperfusion injury and be based on any clinical and preclinical data available.

### **8.7 Transfer to the Heart Attack Centre at St Bartholomew's Hospital**

Patients will be transferred to the Heart Attack Centre at St Bartholomew's Hospital by the two ECMO consultants and London Ambulance Service. The Heart Attack Centre will be pre-alerted using the current systems in process that alert the teams as to whether patients are "self-ventilating" or "ventilated". An additional category of "ECMO supported" will be included.

### **8.8 Post-resuscitation care**

Following arrival at the Heart Attack Centre the care of the patient will be managed by standard algorithms outlined in the Study manual. These will essentially follow the Standard Operating Procedures and Policies of St Bartholomew's hospital. These consider:

- assessment of the need for coronary angiography
- complete versus culprit-only revascularisation
- use of intra-aortic balloon counter-pulsation
- use of therapeutic hypothermia
- haemodynamic management on ECMO
- management of distal leg perfusion
- anticoagulation management
- weaning from VA-ECMO

- general intensive care unit care
- neurological assessment

## 8.9 Schedule of assessments

The time of ECMO blood flow >50% target will be recorded on the CRF.

Many assessments will be made as part of routine clinical practice. These will include computed tomography of the brain, electroencephalograms, somatosensory evoked potentials, markers of kidney, liver, heart and lung function. If these are done, then the results will be recorded in the CRF. They are outlined in Table 2.

In addition, other a variety of physiological, biomarkers, and functional outcome measures, that are not part of routine clinical practice, will be recorded as secondary outcomes for the study as outlined in Table 3.

**Table 2** Standard clinical assessments made that will be included in CRF (if undertaken by clinical team)

Assessment	4 h	24 h	Any time point in 7 d
RIFLE score a		✓	
Computed tomography of brain			✓
Electroencephalography			✓
Somatosensory evoked potentials			✓
Liver function tests b	✓	✓	✓
Echocardiography c			✓
Vital signs d	✓	✓	
Vasoactive medication use e	✓	✓	
Coagulation assessments f	✓	✓	

a The RIFLE score is a classification of acute kidney injury based on creatinine levels and urine output

b Specifically bilirubin, aspartate transaminase, alkaline phosphatase

c A comprehensive study as outlined by the British Society of Echocardiography

d Including heart rate, blood pressure, right atrial pressure, pulmonary artery occlusion pressure, cardiac output and arterial lactate

e Including adrenaline, noradrenaline, dobutamine, dopamine, milrinone, enoximone, levosimendan

f Including prothrombin time, activated partial thromboplastin time, fibrinogen, platelet count

**Table 3** Non-routine assessments made during the study

Assessment	Pre-ECMO	Time of hospital admission				Hospital discharge	90 days
		0 h	24 h	48 h	72 h		
Bilateral pupillometry	✓	✓	✓	✓	✓		
Serum Neuron Specific Enolase		✓	✓	✓	✓		
Plasma/Serum biobanked	✓	✓	✓	✓	✓		
Modified Rankin Scale						✓	✓
Function Independence Measure						✓	✓
EQ-5D							✓

## 8.10 Standard Operating Procedures

The most current standard operating procedures of the Cardiovascular Clinical Trials Unit will be adopted for the conduct of this study. Specific operating procedures have been formulated for other trial activities are outlined in Table 4.

**Table 4** Trial specific Standard Operating Procedures

Name	Version	Date
Using the Functional Independence Measure (FIM)	1.0	20 Aug 2018
Maintaining chain of custody for trial disposables and medical gases	1.0	20 Aug 2018
Maintaining chain of custody for trial samples	1.0	20 Aug 2018
Assessing patients with the modified Rankin Scale	1.0	20 Aug 2018
Assessing patients with the EQ-5D-5L instrument	1.0	20 Aug 2018

Completion of Case Report Forms	1.0	20 Aug 2018
Environmental monitoring of storage areas	1.0	25 Mar 2019
Media and publicity	1.0	01 Mar 2019

## 9. Assessment and management of risk

The details of the risk assessment regarding the study and the mitigating factors put in place are outlined in Table 5.

**Table 5** Risk assessment and mitigation for Sub30 study

Risk details	Initial Assessment*			Mitigating actions	Reassessment		
	PSR	PLR	RRN		PSR	PLR	RRN
Vascular damage during cannulation Large cannula (typically 17-25 Fr) are being inserted into the femoral artery and vein. This may be associated with damage to the vessel and extensive bleeding. Cannulation is likely to be more difficult out of the ICU/operating room due to patient position, weather, and unfamiliar environment	3	3	9	Use of experienced Consultant operators utilising ultrasound for vascular cannulation.	3	2	6
Infection – Local Pre-hospital ECMO is occurring outside a normal operating environment and there is greater risk of environmental contamination of the cannulation site and infection in the patient.	3	3	9	Chlorhexidine preparation of skin. Careful cleaning of cannulation sites on return to hospital environment. Use of prophylactic antibiotics. Aseptic technique. Consideration made for need to re-cannulate at an alternative sterile site on return to Barts Heart Hospital if the access sites were heavily contaminated.	3	2	6
Neurological injury established pre-ECMO Neurological injury may be sustained during the period of cardiac arrest despite bystander CPR.	4	4	16	Use of mechanical compression device to maximise efficacy of chest compressions whilst ECMO instituted. Minimisation of secondary brain injury with avoidance of hyperthermia, consideration of cerebral perfusion pressure, good glycaemic control. In the setting of continued low blood flow further primary brain injury will be minimised by more aggressive cooling. Pre-hospital ECMO is proposed as method of risk reduction for neurological injury in patients who survive.	3	3	9
Bystander interference during cannulation Cannulation will be done surrounded by members of the public and emergency services. Wishing to help they may disrupt the functioning of the cannulation team preventing their effective operation.	3	3	9	Tasking of emergency services to control the environment and bystanders. Utilisation of consultants in pre-hospital care for scene management.	2	1	2
Adverse climate Wind, cold, and rain may make the cannulation difficult.	2	3	6	Use of IPX4 standard equipment if possible to counter effects of rain. Covers utilised for other equipment. Weights for drapes to counter wind Suspension of service if conditions considered too adverse to safely deliver pre-hospital ECMO	2	2	4

Adverse publicity for Trust/Organisations involved An adverse outcome for the patient (severe neurological injury but survival; or death despite significant and prolonged intervention) may be perceived in retrospect as an inappropriate use of healthcare resource (e.g. ICU capacity, blood products).	2	3	6	Discussion with Communications team prior to the event – avoid all public comments until patient outcome known and consent of patient gained. Aim to undertake resuscitation out of public view	2	2	4
Reduced capacity to support other patients Any patient will take up ICU capacity in terms of bed spaces, staffing, and equipment. This may limit the ability to support the work of elective cardiac surgery or emergency respiratory ECMO.	2	3	6	Pre-hospital ECMO team are additional to the standard ECMO team which would not be influenced by the activity. Planning with the theatre schedulers and cardiac surgeons regarding.	2	2	4
Failure to cannulate femoral vessels Expected failure rate of 5-10% of percutaneous cannulation of femoral vessels in cardiac arrest. Failure would negate ability to initiate ECPR.	3	4	12	Experienced consultants, cannulating with the use of ultrasound, Saline fluid infusion to improve vessel size. Augmented reality ultrasound glasses to improve technique. Any failure to cannulate would mean patient would receive standard ongoing care as per LAS resuscitation protocols.	2	4	8
Leg ischaemia – arterial The size of the arterial cannula can impair blood flow to the ipsilateral limb. A distal limb perfusion cannula will be difficult to insert in the pre-hospital environment	3	4	12	Routine insertion of a distal limb perfusing catheter on return to the Barts Health. Use of smaller arterial cannulae (15Fr).	3	2	6
Infection of patients with SARS-CoV-2 There is a risk of healthcare workers infecting the patient. This may occur acutely in the resuscitation and subsequent hospital care but also when the patients are followed up at 90 days.	4	2	8	Research team will wear full respiratory PPE during their attendance at the cardiac arrest and their continuing care until they leave the patient area. Staff at St Bartholomew's hospital wear appropriate PPE for the patient's risk status and never wear less than gloves and surgical face mask for any patient. Research team will be screened for infection (symptoms and temperature) at the start of each shift. Use of video-consultation in follow up (a practice that has been adopted in our critical care service)	4	1	4

Infection of Research Staff with SARS-CoV2 There is a risk of the patient infecting research staff with SARS-CoV-2. Patients with OHCA are more likely to have SARS-CoV-2.
	
3      2
	
6
	
Cleaning and decontamination of LAA fast-response vehicle as part of morning checks Surgical masks to be worn by all team members while in car (except navigator when giving driver instructions on blue lights) Team no longer roaming but based in a (pre-agreed) LAS ambulance station observing all local COVID-19 precautions at said station Formal 'doffing' and decontamination before every patient contact, presuming all patients are a COVID-19 infection risk Consideration of not bringing ECMO equipment and any non-essential equipment into 'Hot zone' near patient until confirmed potential Sub30 patient (Team-leader role to be updated) Additional sealed PPE grab-bag added to equipment and relevant checklists Symptom and temperature check all team members at start of study day If symptoms of COVID-19 develop during a shift then the study day will be cancelled and the team will self-isolate according to current Barts Health NHS Trust guidance. All patients screened for SARS-CoV-2 infection on arrival to hospital, according to Barts Health NHS Trust standard practice. All patients considered to be potentially infected SARS-CoV-3 – so are managed with full aerosol protecting PPE until infection
	
3      1
	
3


Negative impact on staff wellbeing with participation The additional workload or personal risk factors may mean some of the study team no longer wish to participate in the study. Staff are uncomfortable wearing PPE for long periods of time.
	
3      3
	
9
	
Reinforce that all shifts are voluntary and there is no obligation for trained pool to continue in the study. Individual Barts Health NHS Trust COVID-19 risk assessment made prior to any team member joining the study Additional section to shift de-brief form specific to any COVID-19 related concerns or suggestions
	
2      2
	
4

\* PSR – Potential Severity Rating; PLR – Potential Likelihood Rating; RRN – Risk Rating Number (PSR x PLR)

